#### The LYB Yoga intervention

Thirty participants will be randomly selected to participate in the LYB Yoga intervention ([An overview of randomization techniques: An unbiased assessment of outcome in clinical research - PMC \(nih.gov\)](#)). The Yoga sessions will be virtual and study participants will be able to complete these sessions at home. The session will not be recorded. They will be free of cost for the study participants. Yoga that will be taught is a simple form of exercise that is tailored to people with a history of TBI. The movements are slow and study participants will have the choice to participate up to their comfort level. The role of LoveYourBrain will be to administer the yoga intervention and will not be engaged in the research study.

To be included, they should:

1. Have low PTG (PGI-X score <75)
2. Be inexperienced/novice yoga users
3. Not be receiving rehab services (per [name] on 6/12/2023: exclude anyone who is receiving counseling, psychiatry, PM&R, neuro, OT, psychotherapy, social work etc.)

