#### DATA ANALYSIS PLAN

We will initially use univariate analyses and descriptive statistics to examine the frequencies and distributions of the data. Established cut-offs will be used to define the low and high PTG groups, and compare the

distribution of PTG domains, PCS, mood and PTSD between the groups. In bivariate analyses, we will use Chi-square tests ( $\chi^2$ ) to compare differences between the low PTG and high groups across various demographic and injury-related factors. Variables that meet a p-value cutoff of  $p < 0.2$  during the bivariate analyses will be included in adjusted regression models. We are using a  $p < 0.2$  cutoff instead of  $p < 0.05$  to be conservative, since this is the first exploration of PTG outcomes in a female concussion sample that we are aware of. Crude and adjusted logistic regression models will be used for effect estimates and prediction models, using a significance level of  $p < .05$

For Aim 2, we will use paired t-test to compare the mean difference in PTG scores and domains before and after the yoga intervention to determine its effectiveness. We will administer the PTG surveys again at 7 weeks and 30 days to 15 Yoga and 15 Wait list controls (see Figure 5). The 15 Yoga participants will also do the post-yoga assessments at 7 weeks. The 15 Wait list controls will do the LYB program after the 30-day PTG surveys have been completed. The 15 Wait list controls will receive a follow up survey, 1 week after the completion of the LYB program. The intervention group participants who have attended 3 or more LYB yoga sessions will also receive a week-20 follow up survey and the participants who complete the survey will receive \$30 incentive.

To evaluate the feasibility & acceptability of the intervention, we will collect the following metrics:

- A) Overall Yoga intervention **interest rate**=# interested in participating in Yoga/total # participants (how many PINK women are interested in the Yoga overall? If high can speak to using Yoga as an effective intervention for this population. If low, explore reasons)
- B) PTG-specific interest rate: #interested participants with low PTG (score <75)/total #participants (how many people with low PTG are interested in Yoga? We expect this proportion to be lower than overall metric in A above)
- C) Yoga intervention participation rate=# who enroll in LYB program (n=30)/#interested participants with low PTG (We will invite 30 people to participate so we know the numerator)

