- D) Yoga intervention completion rate =# who enroll in LYB program (n=30)/#who complete the LYB intervention
- E) Acceptability of intervention: LYB collects this data at the last session on gratitude so we can get some qualitative data

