#### INCENTIVES

Participants will receive \$40 and the 30 who participate in the Yoga intervention will receive another \$60 for completing all 6 weeks of the intervention.

For the 15 Wait list controls, who participate in the Yoga intervention and complete the follow up survey will receive \$30.

The intervention group participants who have completed 3 or more LYB yoga sessions and who have completed the week-20 follow up survey will receive \$30 incentive.

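### The only direct record of participants' views on the yoga comes from feedback at the provider's last session, so women absent from that session are not heard

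*Combined protocol and SAP*

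**What the plan says.** The DATA ANALYSIS PLAN introduces metrics A to E with "To evaluate the feasibility & acceptability of the intervention, we will collect the following metrics". A and B are interest rates, C is a participation rate and D is a completion rate. E is acceptability, and its full specification is "LYB collects this data at the last session on gratitude so we can get some qualitative data".

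The section on the LYB Yoga intervention fixes the number taking part ("Thirty participants will be randomly selected to participate in the LYB Yoga intervention"). The data analysis plan splits them into 15 yoga participants and 15 wait-list controls who do the programme later. The same intervention section says of the provider: "The role of LoveYourBrain will be to administer the yoga intervention and will not be engaged in the research study".

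Three later contacts with participants are planned, all in the DATA ANALYSIS PLAN:
- **Week 7:** "The 15 Yoga participants will also do the post-yoga assessments at 7 weeks".
- **Week 20:** "The intervention group participants who have attended 3 or more LYB yoga sessions will also receive a week-20 follow up survey".
- **Wait list:** a follow-up survey one week after the programme is completed.

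Under INCENTIVES, the 30 yoga participants receive a further $60 "for completing all 6 weeks of the intervention". The $30 for the wait-list survey goes to wait-list women who take part in the yoga and complete that survey.

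**The concern.** Attendance at the last session decides who is heard under metric E. It is reasonable to expect that women who have gone by then differ in their view of the programme from those still present, so feedback from the second group alone need not represent all who enrolled.

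What is at stake is the pilot's use for planning. The limitations section says a larger study, ideally a clinical trial, is needed. Why women stop, and what those who stopped thought of the sessions, is among the most useful things a pilot can pass on to that study. It is hard to recover afterwards.

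A secondary matter is that the feedback is gathered by the organisation delivering the programme, which the protocol places outside the research.

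**Working it through.** The plan states no acceptability figure, so there is nothing to reproduce. The check is a reading of every point at which a woman who left early, or missed the last session, could give her view.

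| Source | Who is reached | Acceptability views or reasons for stopping? |
|---|---|---|
| Metrics A, B | Survey respondents, before the yoga | Interest only. The remark about looking into reasons concerns low interest, not leaving |
| Metric C | Women invited to the yoga | A count |
| Metric D | All enrolled | Counts of enrolled and completers; no opinions |
| Metric E | Women at the last session | Yes, qualitative, gathered by the provider |
| 7-week post-yoga assessment | The 15 yoga women, no attendance condition | Content not described; not linked to metric E |
| Wait-list follow-up survey | The 15 wait-list women, timed from completion | Content not described |
| Week-20 survey | Intervention-group women with 3 or more sessions | Content not described; the earliest leavers are excluded |

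Three things follow.

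1. E is the only row that records opinions of the yoga, and it is filtered by presence at one session. A woman who attended most sessions but missed the last is lost. One who skipped several but came to the last is heard.
2. The plan expects some women not to finish: it has a completion metric, a 3-session threshold and a payment tied to completing all 6 weeks. It describes no route by which a woman who stops can say why.
3. Metric D, as written, does not show how selected the metric E respondents are. It reads "Yoga intervention completion rate =# who enroll in LYB program (n=30)/#who complete the LYB intervention". With enrolment as the numerator, the ratio is always 1 or more and cannot be read as a completion proportion, although both counts are available.

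**How much could be missing.** No attendance figure is given, so the following last-session attendances are assumptions. The share of enrolled women unheard is (30 − attending)/30.

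- 27 attend: 3/30 = 10%
- 24 attend: 6/30 = 20%
- 21 attend: 9/30 = 30%
- 15 attend: 15/30 = 50%

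Suppose further that views could be coded as favourable or not. The favourable share among all 30 would then lie between (favourable attenders)/30 and (favourable attenders + absentees)/30.

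- 27 attend, 24 favourable: observed 24/27 = 89%; possible range 24/30 = 80% to 27/30 = 90%.
- 15 attend, 14 favourable: observed 14/15 = 93%; possible range 14/30 = 47% to 29/30 = 97%.

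These ranges show only how much the unheard views leave open. They do not estimate a bias in this study.

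**The case against.** The strongest reply is that metric E promises qualitative material and nothing more. No rate, denominator, threshold or go/no-go rule depends on it, acceptability is not among Aims 1a to 2b, and no planned inference on PTG uses it. All of that stands, and it limits the weight of the point. It does not change who is left out, since selection shapes qualitative themes as well as percentages.

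Some stronger readings are tempting but not supported.

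- **A reader might infer a measurable overstatement**, for example 90% reported against 70% true. Any such pair rests wholly on assumed attendance and satisfaction, for a quantity the plan does not compute.
- **A reader might infer that reasons for stopping will not be collected.** The content of the 7-week, wait-list and week-20 surveys is not described, and the project schematic (Figure 5) is not visible in the text reviewed. The supportable statement is that no such collection is described.
- **A reader might infer that women leave because yoga does not suit them, or that the gratitude theme draws favourable answers.** The documents give no reasons for leaving and do not say whether feedback is anonymous, written or spoken. The $60 payment could also keep some dissatisfied women to the end, where they would be heard.
- **A reader might infer that early leavers are invisible to the whole evaluation.** They are not: metric D's counts include everyone enrolled. Only their views are missing.
- **A reader might infer that the provider has become a research data collector in breach of the protocol.** The line can equally mean that the provider gathers routine feedback of its own, which the study then obtains. The two statements need reconciling, no more.

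**Conclusion.** The point holds as a flaw in how acceptability is collected. Metric E is the only metric that directly records participants' views of the intervention. It draws on qualitative feedback gathered by the provider at the last session, and nothing else in the documents describes asking absent women for their views or their reasons for stopping.

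The likely effect is a more favourable picture. That direction rests on the assumption that absentees are on average less satisfied than attenders, which is plausible but not shown by the documents. No size can be attached. The exclusion itself needs no assumption, as it follows from the wording of metric E.

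The consequence is confined to the pilot's acceptability findings and their use in planning a larger study. The PTG comparisons are unaffected. The change is worth making before the yoga sessions begin because it is cheap and the information is difficult to obtain later.

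**What to change.** 1. Add a short set of acceptability items and one reason-for-stopping item to the study's own surveys: the 7-week post-yoga assessment for the 15 yoga women and the follow-up survey for the 15 wait-list women.
2. Send them to all 30 enrolled women whatever their attendance.
3. Time the wait-list survey from the scheduled end of the programme rather than from individual completion, so that a woman who stopped still receives it.
4. Check that the wording of the $30 wait-list incentive does not exclude women who stopped early.
5. Report the number responding out of the number enrolled, by group.
6. Keep the provider's last-session comments as supplementary material, and add a sentence reconciling their use with the statement that the provider is not engaged in the research.

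**Cost.** A few extra items on surveys already planned, a slight increase in respondent burden, and edits to the survey timing and incentive text. The incentive outlay may rise a little if early leavers become eligible. The acceptability findings may be less favourable. No new visit, arm or sample size is needed.

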#### POWER AND SAMPLE SIZE (based on PTG prevalence)

Using a low PTG prevalence of 35%, an alpha of 0.05 and 95% confidence interval, a sample size of 350 will provide sufficient power of 80% for the intended analyses.

#### INCENTIVES

Participants will receive \$40 and the 30 who participate in the Yoga intervention will receive another \$60 for completing all 6 weeks of the intervention.

For the 15 Wait list controls, who participate in the Yoga intervention and complete the follow up survey will receive \$30.

The intervention group participants who have completed 3 or more LYB yoga sessions and who have completed the week-20 follow up survey will receive \$30 incentive.

## LIMITATIONS OF THE STUDY

First and foremost, this study is limited to female concussion survivors only and as such, is not generalizable to men who experience TBI. Secondly, the study is recruiting from the PINK concussion group, so the study cannot be generalizable to anyone not in this group, and/or all females with TBI. As this is a pilot, the Yoga intervention will have only 30 participants therefore there's the potential for Type 2 error (false negatives). We will need a larger, more powered study -ideally a clinical trial-to determine the true effect of the Yoga intervention.

